Non-inferiority unblinded randomized controlled trial where subjects will be randomized in a ratio of 1:1 to Dilapan-S[®] and misoprostol groups. We decided to use the non-inferiority design as Misoprostol is considered as one of the accepted and standard treatments for induction of labor in United States. Our assumptions for the trial are based on results of PROBAAT-II trial, a large well designed randomized trial conducted in EU for studying efficacy of mechanical and pharmacological methods for labor induction. Assuming a rate of vaginal delivery within 36 hours to be 65% for Misoprostol and 71% for mechanical method (based on data on transcervical Foley catheter in PROBAAT-II [3] and a recent trial comparing Foley catheter to Dilapan-S[®] for cervical ripening done by Saad et al. [12]), with a non-inferiority margin of 10 % and an expected screen failures rate of 5%, a total of 322 subjects will need to be randomized in ratio 1:1 to Dilapan-S[®] vs Misoprostol group. 153 eligible and assessable subjects are needed in Dilapan-S[®] group and 153 in Misoprostol group for analysis. The study is powered at 85% for detecting the primary outcome with a type 1 error at 2.5% for one-sided test.

Objective for the trial

To assess efficacy of cervical ripening with Dilapan-S[®] or Misoprostol in women undergoing induction of labor.

Primary research question (primary endpoint)

Proportion of subjects achieving vaginal delivery within 36 hours after the initiation of the cervical ripening in Misoprostol and Dilapan-S[®] group.

Rationale: The authors of PROBAAT-II study make the valid point that as an outcome of labor induction, giving birth vaginally is more important than how quickly it happens; therefore 24 hours may not be a long enough time for appropriate assessment. Indeed, the effect found in the PROBAAT-II study would have been reversed had the outcome been measured by assessing vaginal delivery within 36 hours. There is therefore a call to standardize the outcome measure in IOL trials to a vaginal delivery within 36 hours [6], particularly when mechanical methods are employed.

Secondary research questions (secondary endpoints)

- Bishop score at 12 hours after the intervention
- Percentage of subjects delivering vaginally in 24 hours after the initiation of intervention
- Overall vaginal delivery rate in each group
- Rate of operative deliveries
- Rate of cesarean deliveries in each group.
- Total length of hospital stay

Maternal outcomes:

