- 1. Onset of spontaneous labor (defined as regular painful uterine contractions with a dilation of ≥ 4 cm and effacement of 75% or more)
- 2. Vaginal bleeding
- 3. Persistent Category 2 or Category 3 fetal heart tracing
- 4. Spontaneous rupture of membranes
- 5. Spontaneous expulsion of Dilapan-S[®] rods (*if Bishop score is still <6, another set of rods may be placed and allowed to remain in situ for a maximum of 12 hours cumulative based on clinical assessment made by the supervising provider*)
- 6. AROM is indicated

Labor Induction

Subjects in both groups will have an assessment of Bishop score 12 hours after the study intervention and evaluated for amniotomy and Oxytocin infusion. Oxytocin will be initiated as per the institutional guidelines. Amniotomy will be undertaken as soon as clinically feasible. If after 24 hours of amniotomy with Oxytocin the patient is not in active labor [cervical dilatation<6 cm], a diagnosis of failed induction will be made [Appendix 2] and a decision will be made to proceed with cesarean section. During labor, decision to proceed with operative delivery or cesarean section will be made by the attending physician supervising the care of the patient. All subjects will have the option to receive epidural during labor for pain management.

COLUMBIA UNIVERSITY College of Physicians and Surgeons

Oxytocin administration CUMC:

Oxytocin will be administered for labor induction and augmentation as per the institutional guidelines [Appendix 2]. Oxytocin is supplied to L&D unit in prepared bags with 30 units of Oxytocin in 500 cc of Normal Saline. Oxytocin will be initiated at 1 milliunit/minute and increased every 15 minutes, till an optimal response is obtained.

The maximum dose is limited to 40 milliunits/minute.

UTMB:

Oxytocin will be administered for labor induction and augmentation as per the institutional guidelines [Appendix 3]. Oxytocin is supplied to L&D unit in prepared bags with 20 units of Oxytocin in 1000 cc of Lactated Ringers. Oxytocin will be initiated at 2 milliunit/minute and increased every 20 minutes, till an optimal response is obtained. The maximum dose is limited to 40 milliunits/minute.

Delivery period

Data for date, time and mode of delivery and intra-partum complications (incl. those found during induction period) will be collected. The complications will include, but are not limited to following:

- Uterine tachysystole (defined as > 5 contractions per 10 minutes averaged over 30 minutes.

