# 3.2. SECONDARY OUTCOMES

Individual and composite maternal and fetal outcomes including overall vaginal delivery rate, cesarean section rate, Bishop score after cervical ripening, infections, postpartum hemorrhage. Neonatal outcomes include Apgar scores, NICU admission and sepsis.

Secondary endpoints are:

- Overall vaginal delivery rate in each group
- Rate of caesarean deliveries in each group
- Rate of operative deliveries (vaginal plus caesarean)
- Bishop score at 12 hours after the intervention and change in Bishop score
- Percentage of subjects who did not receive all 6 misoprostol doses
- Percentage of subjects with failed Dilapan-S insertion
- Percentage of subjects delivering vaginally in 24 hours after the initiation of intervention

- Delivery time
- Initiation of cervical ripening to delivery time
- Initiation of oxytocin to delivery time
- Total length of hospital stay
- Maternal outcomes:
  - Chorioamnionitis
  - Endometritis within 2 weeks after delivery
  - Postpartum haemorrhage (EBL>1000cc and/or drop in HCT by 10 points)
  - 3rd and 4th degree lacerations
- Neonatal outcomes:
  - Apgar score <7 at 5 min
  - Cord arterial blood pH and Cord arterial blood pH <7
  - Cord arterial blood base excess and Cord arterial blood base excess > -12mmol/l
  - NICU admission within 2 weeks after study intervention
  - Antibiotic use within 2 weeks after study intervention

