#### 7.2. ANALYSIS OF THE PRIMARY ENDPOINT

The primary outcome is the proportion of subjects achieving vaginal delivery within 36 hours after the initiation of the cervical ripening in Misoprostol and Dilapan-S® groups. Proportion of patients in each group and their difference will be calculated. One-sided 97.5% confidence interval adjusted for the stratification factors (parity and gestational age) will be calculated for the difference in the proportions and conclusion about non-inferiority will be drawn from it taking into consideration a 10% non-inferiority margin. Unadjusted confidence interval will be calculated as well.

Additionally, the primary outcome will be analysed for each stratification factor. Mantel-Haenszel test will be used to test the difference between the subgroups.

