#### 7.3. ANALYSIS OF SECONDARY ENDPOINTS

All quantitative secondary variables will be summarized separately for each arm. Means of the two treatment arms will be compared with two-sample t-test and Wilcoxon rank-sum test as appropriate.

All secondary variables involving rates and percentages, will be calculated for both arms. Difference in proportions will be derived together with a 95% two-sided confidence interval. The difference between treatment groups will be concluded if the confidence interval does not include zero.

Maternal and neonatal outcomes will be summarized as reported in the CRF.

Delivery time will be presented using Kaplan-Meier curves with censoring for caesarean delivery.

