#### Efficacy data

Table	14.2.1	Summary of Delivery Characteristics
Table	14.2.2.1	Primary analysis for proportion of Vaginal Delivery within 36 hours
Table	14.2.2.2	Analysis for proportion of Vaginal Delivery within 24 hours
Table	14.2.3.1	Analysis for proportion of Mode of Delivery
Table	14.2.3.2	Analysis of Delivery Time
Table	14.2.4.1	Analysis of Bishop score
Table	14.2.5.1	Analysis of Total Length of Hospital Stay
Table	14.2.6.1	Summary statistics of Maternal Outcomes
Table	14.2.7.1	Summary statistics of Neonatal outcomes

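### The planned Kaplan-Meier curves censor caesareans, a competing event, so they can read above the trial's own 24- and 36-hour vaginal delivery proportions

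*SAP*

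**What the plan says.** The only instruction on how the time-to-delivery display is built is in SAP 7.3: "Delivery time will be presented using Kaplan-Meier curves with censoring for caesarean delivery". Neither document mentions cumulative incidence or a competing-risk method, or labels the curve as cause-specific. No log-rank test, hazard ratio or median is planned from it.

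The trial's other measures of timely vaginal delivery are simple proportions. SAP 7.2 defines the primary outcome as the "proportion of subjects achieving vaginal delivery within 36 hours after the initiation of the cervical ripening", and SAP 3.2 lists "Percentage of subjects delivering vaginally in 24 hours after the initiation of intervention" as a secondary endpoint. SAP 6.2.2 makes all randomised women the primary efficacy population, so a woman delivered by caesarean stays in the denominator as a non-success. The SAP's efficacy table list carries both results: Table 14.2.2.1, "Primary analysis for proportion of Vaginal Delivery within 36 hours", and Table 14.2.2.2, "Analysis for proportion of Vaginal Delivery within 24 hours".

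The protocol's Labor Induction section describes two routes to caesarean. One is failed induction ("If after 24 hours of amniotomy with Oxytocin the patient is not in active labor"). The other is the attending physician's decision during labor, which has no fixed time.

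**The concern.** Kaplan-Meier censoring is meant for people whose event has not been seen but could still occur, at the same rate as in those still under observation. After a caesarean, vaginal delivery can no longer occur. The censoring is also informative: failed-induction caesareans are done because labor has not progressed, so these women cannot be taken as typical of those still undelivered.

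The curve drops these women from the risk set, whereas the 24- and 36-hour proportions count them as non-successes. One report could therefore give two vaginal delivery figures at the same hour, with nothing planned to explain the difference. The visual gap between arms can also shrink or widen, depending on how many caesareans each arm has and when.

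**Working it through.** **Inputs.** Protocol, Study Design: "Assuming a rate of vaginal delivery within 36 hours to be 65% for Misoprostol and 71% for mechanical method", a 10-point margin, one-sided 2.5% error, 85% power and 153 assessable women per arm. These rates reproduce the plan's sample size: (0.65×0.35 + 0.71×0.29) × (1.960 + 1.036)² / (0.06 + 0.10)² = 152.0, hence 153 per arm with rounding up (power at 153 is 85.2%), and 306/0.95 = 322.1 against the stated 322. So 65% and 71% serve below as the true 36-hour proportions. Caesarean incidence and timing are not in the documents and are assumed throughout.

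**Notation.** By time *t*, *v* is the proportion delivered vaginally and *c* the proportion delivered by caesarean. With complete follow-up to delivery, the crude proportion and the Aalen-Johansen estimate both equal *v*.

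**Step 1: limits that need no timing model.** If every caesarean by *t* follows the last vaginal delivery in the window, 1−KM = *v*, with no excess. If every caesarean precedes the first, 1−KM = *v*/(1−*c*). With *c* = 20% at 36 hours the upper limits are 0.65/0.80 = 81.3% and 0.71/0.80 = 88.8%. The curve is therefore never below the crude proportion, and timing decides how far above it lies.

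**Step 2: caesareans in proportion to vaginal deliveries throughout.** With proportional cause-specific hazards,

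1−KM = 1 − (1 − *v* − *c*)^(*v*/(*v*+*c*)).

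Example: *v* = 0.65 and *c* = 0.20 give 1 − 0.15^0.7647 = 76.6%.

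| Caesarean by 36 h (assumed) | Misoprostol, true 65% | Dilapan-S, true 71% |
|---|---|---|
| 10% | 69.9% (+4.9) | 76.7% (+5.7) |
| 15% | 73.0% (+8.0) | 80.3% (+9.3) |
| 20% | 76.6% (+11.6) | 84.7% (+13.7) |

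**Step 3: late caesareans.** Vaginal delivery time is taken as normal, mean 24 h, SD 8 h, in both arms. The eventual vaginal share is set to give the planned 36-hour rate: 0.65/Φ(1.5) = 0.65/0.9332 = 69.7%, and 0.71/0.9332 = 76.1%. All other women have a caesarean, so the implied eventual caesarean rates are 30.3% and 23.9%. Caesarean time is normal with the mean and SD shown. With *f_v* the density of vaginal delivery time and *S* the proportion undelivered, 1−KM(*t*) = 1 − exp(−∫ *f_v*/*S*), integrated numerically.

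| Caesarean time, mean (SD) | 36 h, misoprostol (true 65%) | 36 h, Dilapan-S (true 71%) |
|---|---|---|
| 36 h (8 h) | 69.5% | 75.1% |
| 36 h (6 h) | 68.5% | 74.3% |
| 40 h (6 h) | 66.2% | 72.1% |
| 42 h (6 h) | 65.6% | 71.6% |

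With mean 36 h and SD 6 h, the 24-hour excess is 0.1 point in each arm (0.2 to 0.3 with SD 8 h). At 48 h the curves read 82.8% against a true 69.6%, and 88.3% against 76.0%: 13.2 and 12.3 points high.

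**Step 4: the gap between arms.** Under Step 2, the true 6-point gap reads 80.3 − 76.6 = 3.7 with 20% caesareans on misoprostol and 15% on Dilapan-S, and 80.3 − 73.0 = 7.3 with 15% in both. If both arms were truly at 65%, with caesareans at 10% and 20%, a false gap of 76.56 − 69.92 = 6.6 points would appear. In Step 3 (SD 6 h) the gap hardly moves: 74.3 − 68.5 = 5.8 with mean 36 h and 72.1 − 66.2 = 5.9 with mean 40 h.

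**The case against.** The strongest reply concerns size. A woman who completes 12 hours of ripening and then 24 hours of amniotomy with oxytocin reaches a failed-induction caesarean at about 36 hours or later. Such cases add almost nothing at 24 hours and little at 36. That stands, and the late-caesarean table shows it. The larger figures need earlier caesareans, which the protocol allows by physician decision during labor but does not quantify. The distortion of the gap appears under proportional hazards and hardly at all in the late-caesarean cases. The large 48-hour excess depends on the implied 24–30% eventual caesarean rates, and 48 hours is not a planned endpoint.

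The curve is also only a display, and the correct 24- and 36-hour proportions have their own tables. That limits the consequence. A caesarean-censored curve can be defended as a cause-specific description, but only if labelled as such, which the SAP does not do.

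Two limits on the comparison also stand. The SAP lists tables but no figures, so where the curve will appear is unknown. It also gives delivery time no origin, listing it separately from ripening-to-delivery and oxytocin-to-delivery time. Reading the curve at 24 or 36 hours against the tables makes sense only if it starts at ripening. None of this removes the upward bias when the curve is read as the proportion delivered vaginally.

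**Conclusion.** The concern holds. As written, the display does not estimate the proportion of women delivered vaginally by a given time, and it can only err upward. The direction is certain, given complete follow-up to delivery. The size is not, because it depends on caesarean incidence and timing that the documents do not give. In the cases examined, the 36-hour excess runs from 0.6 point (caesareans centred on 42 hours) to nearly 14 points (20% by 36 hours under proportional hazards). It is zero if every caesarean comes after the window. At 24 hours it is small unless caesareans come early.

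This should be corrected but is of modest weight: the sample size, primary estimate, confidence interval and non-inferiority conclusion do not depend on the curve.

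**What to change.** In SAP 7.3, replace the sentence on the curves with:

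> Time from initiation of cervical ripening to vaginal delivery will be presented by arm as cumulative incidence (Aalen-Johansen) curves, with caesarean delivery as a competing event.

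With complete follow-up these curves pass exactly through the crude 24- and 36-hour proportions, so figure and tables agree. The wording also fixes the time origin that the SAP leaves open for delivery time; the authors should confirm that choice. Gray's test is optional, as is a summary of ripening-to-delivery time by mode of delivery. If the Kaplan-Meier curve is kept as well, label it cause-specific and state that it does not estimate the proportion delivered vaginally.

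The cost is one SAP sentence. The method is available in SAS 9.4 and uses delivery time and mode, which are already collected.

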#### 7.4. SAFETY ANALYSIS

Exploratory variables will be evaluated from the adverse event and device deficiency reports. Number of cases and proportion of patients will be presented.

<sup>1 Lower limit of two-sided 95% confidence interval is same as using one-sided 97.5% confidence interval.

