- Chorioamnionitis
- Endometritis within 2 weeks after delivery,
- Postpartum hemorrhage (EBL>1000cc /and or drop in HCT by 10 points) **Neonatal outcomes:**
- Apgar score <7 at 5 min
- Cord Arterial blood pH <7
- Base excess >12mmol/l
- NICU admission within 2 weeks after delivery
- Antibiotic use within 2 weeks after delivery

Exploratory research questions (exploratory endpoints)

There is paucity of clinical data in the literature obtained through well designed clinical trials for Dilapan-S[®] use for cervical ripening in women undergoing induction of labor. We would like to collect following information for assessing safety of Dilapan-S[®] use when compared to Misoprostol. Similar information was collected by Saad et al. [12] in their recent randomized trial comparing efficacy of Dilapan-S[®] to Foley catheter for cervical ripening. These are known potential complications of planned interventions and include (but are not limited to) the following:

Undesirable side effects

- Fever, nausea, vomiting and diarrhea
- Uterine tachysystole
- Hyperstimulation
- Uterine hypertonus
- Failed induction of labor, arrest of first and second stage of labor

Complications specific to dilator insertion

- Vaginal bleeding
- Rupture of membranes
- Cervical laceration
- Excessive pain causing need for analgesia during cervical ripening
- Vasovagal reaction during insertion of the device
- Entrapment of the device
- Fragmentation of device during removal or insertion
- Retraction of device into uterine cavity.

Study subjects inclusion criteria

- 1. Women undergoing labor induction with a gestation of ≥37 weeks determined by best clinical and/or ultrasound estimation
- 2. Live fetus with in cephalic presentation
- 3. Singleton pregnancy
- 4. Able to provide informed consent for participation in the study.

Study subjects exclusion criteria

- 1. Contraindication for vaginal delivery
- 2. Age less than 18 years
- 3. Prior uterine scar from a cesarean section or myomectomy
- 4. Patients who have HELLP syndrome or eclampsia
- 5. Active genital herpes at the time of labor induction
- 6. Complex medical problems that may require assistance with second stage of labor
- 7. Bishop score ≥ 6
- 8. Major fetal congenital anomalies (as assessed by investigator)
- 9. Premature rupture of membranes

Pre-randomization training

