- Hyperstimulation (defined as > 5 contractions averaged over 20 min with abnormal fetal heart changes)[3]
- Uterine hypertonus (defined as a single contraction lasting at least 2 minutes.
- Failed induction of labor, arrest of first and second stage of labor (see Appendix 2) (defined according to the US NICHD, ACOG and SMFM workgroup guidelines [9]
- Intrapartum fever

(defined as body temperature (skin or oral) of 39°C at one reading or as body temperature of 38-38.9°C which persists when retaken after 30 minutes) [13]

Intrapartum fever when present with any of the following indicates infection may be present.

- 1. Purulent discharge on speculum exam from the cervical canal
- 2. Fetal tachycardia lasting more than 10 minutes
- 3. Maternal WBC count of more than 15 K
- 4. Amniotic fluid analysis results indicative of an infection

Postpartum and FU procedures

All participants will receive routine postpartum care. They will be asked to fill out a questionnaire (Appendix 4) in the postpartum period regarding their experience with the cervical ripening method.

All study participants will be contacted via phone two weeks after delivery to find out if they or their baby had any postpartum complication and received treatment at any health care entity other than the hospital where they were admitted for delivery.

Columbia University College of Physicians and Surgeons

Safety reporting

Scope

In relation to the **Dilapan-S**[®], the Clinical Trial is a post-market clinical follow-up study (PMCF) conducted using CE marked device within its intended use. The provisions of Directive 93/42/EEC concerning information and notification of incidents occurring following placing devices on the market are fully applicable. Medical Device Reporting regulation (21 CFR 803) will be followed to report certain device related adverse events and product problems to the FDA.

The Investigator shall ensure that Funder will be informed about any SAE that would be related to study device according to the definitions given below. Complaints about any Product Problem are within the scope of obligatory notification too, incl. product defects, malfunctions or user errors.

AEs not related to the study device are not to be reported to Funder. Borderline events should be handled conservatively and the Funder should be notified in case of any doubt.

Definitions

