Adverse Event (AE) is any untoward medical occurrence in a subject and that does not necessarily have a causal relationship to the study device and study procedure.

Serious Adverse Event (SAE) is any AE that:

- Results in death;
- Is Life-threatening;
- Leads to Hospitalization
- Causes Disability and/or Permanent impairment of a body function or structure;
- Requires medical or surgical intervention to prevent permanent impairment of a body function or permanent damage to a body structure
- Leads to fetal demise, a congenital abnormality, or birth defect.

Product Problem includes:

- Inadequacy of a medical device with respect to its identity, quality, durability, reliability, safety or performance. It also includes inadequate labelling.
- Malfunction: Failure of an investigational medical device to perform in accordance with its intended purpose when used in accordance with the instructions for use or Clinical Investigation Plan.
- User error: Act or omission of an act that results in a different medical device response than intended by the manufacturer or expected by the user.

Evaluation of an AE

When evaluating AEs, the Investigator must determine:

- if the event is serious. Seriousness criteria are based on definition of an SAE (above).
- if the event is related to the study device. The following rules are to be applied:
 - a) **Not Related**: AE which are clearly and unquestionably due to causes other than the study device (e.g., concomitant disease).
 - b) **Related**: AE which are felt with a reasonable degree of certainty to be related to the study device.

c) **Unknown**: AEs for which a connection with the study device cannot be ruled-out with certainty, or not enough information is available to assess the relationship.

Confidentiality of Study Data

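### The safety endpoints are counted from adverse event and device deficiency reports, although the protocol already collects the main labour complications as delivery data in both arms

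*SAP*

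**What the plan says.** SAP 3.3 lists the safety endpoints in two groups: undesirable side effects (3.3.1) and complications specific to dilator insertion (3.3.2). The protocol calls the corresponding items exploratory endpoints. SAP 7.4 names their source: "Exploratory variables will be evaluated from the adverse event and device deficiency reports". The output is descriptive: "Number of cases and proportion of patients will be presented". The protocol's Biostatistics section, under Exploratory variables, carries the same rule.

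The protocol's purpose for these endpoints is comparative. Its Exploratory research questions section begins "We would like to collect following information for assessing safety of" Dilapan-S and sets this against misoprostol.

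The protocol's Delivery period section describes a second body of data on the same kind of event: "Data for date, time and mode of delivery and intra-partum complications (incl. those found during induction period) will be collected". This is not restricted to one arm. The list that follows gives working definitions, for example "Uterine tachysystole (defined as > 5 contractions per 10 minutes averaged over 30 minutes".

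For maternal and neonatal outcomes, by contrast, SAP 7.3 names the CRF as the source.

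**The concern.** Several safety endpoints are ordinary events or outcomes of labour. Whether a long run of contractions, a failed induction or an arrest of labour becomes an adverse event report depends on someone judging it reportable. A CRF item tied to a written definition leaves less room for that judgement.

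Two features of the trial make this matter. First, staff know the allocation, so the decision to report is made with the arm in view. Second, the protocol's Safety reporting section is written from the device's side: its scope is Dilapan-S, and the investigator decides only "if the event is related to the study device". No matching assessment for misoprostol is described. In the misoprostol arm, tachysystole, hyperstimulation and fetal heart abnormalities are reasons to hold a dose, so they may be charted as routine management and never filed as adverse events.

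At stake is the comparison of side effects between arms. The protocol's rationale claims a lower risk of tachysystole and hyperstimulation with Dilapan-S, and these are among the events whose count depends on the source chosen.

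**Working it through.** The documents give no expected rate, count or precision for the safety endpoints, so there is no figure to reproduce. The check is a comparison of passages.

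**1. Do the two sources cover the same events?** SAP 3.3.1 against the protocol's Delivery period list:

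| SAP 3.3.1 endpoint | In the delivery list? | Definition given there |
|---|---|---|
| Uterine tachysystole | Yes | Contraction count averaged over 30 minutes |
| Hyperstimulation | Yes | Contraction count over 20 minutes with fetal heart changes |
| Uterine hypertonus | Yes | One contraction of at least 2 minutes |
| Failed induction, arrest of labour | Yes | By reference to Appendix 2 and workgroup guidelines |
| Intrapartum fever | Yes | 39°C once, or 38 to 38.9°C persisting at 30 minutes |
| Nausea, vomiting, diarrhoea | Not named | None |
| Abnormal fetal heart tracing during ripening | Not named | None |

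The delivery list is expressly not exhaustive, so an item not named may still have a CRF field. None of the SAP 3.3.2 complications is named there. The protocol does record the number of rods inserted (Pre-induction, Arm A).

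**2. Which source governs?** SAP 7.4 and the protocol name the reports alone. Neither mentions the delivery data for these endpoints, or says what happens if the two disagree.

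**3. Do the planned outputs match the named source?** SAP 6.1 says all collected data will be listed. The listings include pre-induction data (16.2.4.3) and delivery data (16.2.4.4). There is none for adverse events or device deficiencies. Safety Tables 14.3.1 and 14.3.2 therefore have no listing of the source named in 7.4.

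**4. What could incomplete reporting do?** Let p be the true event rate in an arm and c the fraction of events that reach a report, assuming no false reports. The observed rate is p × c, and the observed difference (Dilapan-S, D, minus misoprostol, M) is

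pD × cD − pM × cM.

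- If cD = cM = c, this equals c × (pD − pM). Both rates are too low and any true difference shrinks.
- If pD = pM = p but capture differs, it equals p × (cD − cM). The arm with fuller reporting looks worse.

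The documents supply neither p nor c for either arm, so neither the size nor the direction of any error can be calculated.

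**The case against.** A reader might infer that adverse event reports here are a device-only source, so that misoprostol events are left out or under-counted. The documents do not support that:

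- The protocol's Definitions cover any unwanted medical event in a participant, with no causal link to the device required. Misoprostol-treated women are included, and they are in the safety population (SAP 6.2.1).
- The rule that begins "AEs not related to the study device are" goes on to say that such events are not reported to the Funder. It limits notification to the Funder and does not restrict recording at the site or analysis.
- Relatedness does not filter the counts. SAP 7.4 presents cases and proportions whatever the causality grade, so device-only grading does not itself remove a misoprostol event.
- Unrelated events in the Dilapan-S arm could be missed as well, so any loss need not differ between arms.

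It can also be argued that the reports are not a separate pathway. SAP section 2 says data come from chart review, the CRF is not available, and the missing listing could mean that these events sit in the pre-induction and delivery datasets. That is possible, but the text would then need to say so.

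Finally, the endpoints are exploratory and descriptive, and chorioamnionitis, endometritis, postpartum haemorrhage and the neonatal outcomes already come from the CRF. All of this stands. It limits the point to one of source and traceability without removing it.

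**Conclusion.** The point holds as a weakness in the stated data source. Both documents name only adverse event and device deficiency reports, while five of the seven entries in SAP 3.3.1 appear in delivery data collected in both arms, mostly with definitions. The source that is named has no listing.

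Differential under-counting of misoprostol events is a credible risk in an unblinded trial with device-centred safety rules. It is not a demonstrated error, and incomplete reporting could instead lower both rates. No magnitude is given, because any figure would rest on assumed event rates and capture fractions.

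The primary endpoint, its analysis and the sample size are unaffected. The conclusion assumes that the delivery-period items are recorded in the same way in both arms, as the protocol's wording implies; the CRF should be checked to confirm it. Delivery data are also charted by unblinded staff, so changing the source reduces the dependence on judgement but does not abolish it.

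**What to change.** Amend SAP 7.4 and the protocol's sentence under Exploratory variables together; changing one alone would create a conflict between them.

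- **Events possible in either arm:** derive them from the pre-induction and delivery CRF data, using the definitions in the protocol's Delivery period section.
- **Adverse event reports:** use them as a supplement reconciled against the CRF, and as the source where no CRF field exists. Confirm this for nausea, vomiting, diarrhoea, cervical laceration, excessive pain and vasovagal reaction. The same check is sensible for abnormal fetal heart tracing, vaginal bleeding and rupture of membranes, which the delivery list does not name.
- **Device deficiency reports:** keep them for entrapment, fragmentation and retraction.
- **Failed insertion:** take it from the pre-induction data, since it is also a secondary endpoint in SAP 3.2.
- **Listings:** add one for adverse events and one for device deficiencies.

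No new data item is needed where CRF fields exist. That matters because SAP 4.1 describes a safety board review in the past tense, so data had already accrued. The cost is revised wording, a little more programming, and reconciliation of the two sources.
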